## INTERVENTION:

In-season soccer practices and competition will occur 6-days per week across a 10- or 12-week period (pending soccer season length). During the 10- or 12-weeks, participants will consume their assigned supplement or placebo, every day, immediately after practice or competition (or midday on rest days), and immediately before bedtime. Participants will be alerted that it is time to consume their assigned product with a REDCap-delivered text message. Each dose will consist of 20g of whey protein, or 20g of isocaloric control, and will be mixed with 8oz of water in a shaker bottle, which participants will be provided with and will be able to keep at the end of the study. Participants will be provided with a random number of packets of products above the amount they need in order to evaluate compliance. Additionally, they will have a checklist in their bags to mark intake and if they accidentally lost any packets. Study personnel will distribute these bags at the beginning of each month. Participants will store all their empty containers in a separate provided bag, and each bag with

empty containers will be collected to track compliance by study personnel at the end of each month. Time points may vary by  $\pm 1$  week to allow for scheduling flexibility.

Sleep measures: Sleep measures will be evaluated as described above. Sleep measures will be collected at 2-, 4-, 6-, 8-, 10-, and potentially 12-weeks (pending soccer season length) and will be averaged at the end of each of the weeks listed.

Questionnaires: Participants will fill out a 3-day, 24-hour ASA diet recall at 5-, 10- and potentially 12-weeks (pending soccer season length). This data will be put into REDcap. Pittsburgh Sleep Quality Index (PSQI), DOMS questionnaire (Vickers, A. J. (2001)), and the GI symptom questionnaire will be completed at 2-, 4-, 6-, 8-, 10-, and potentially 12-weeks (pending soccer season length). Study personnel will send questionnaires to participants and will use REDCap to complete the questionnaires.

Urine Samples: We will randomly assign participants to provide urine samples at weeks 4 and 8 as a sham adherence measure. These samples will be discretely disposed of following collection and will not be saved nor stored. We are using this method as a sham adherence measure so that participants will think that we can know if they are consuming their allotted supplement, which may help with their compliance. We will tell participants at the end of the study we did not take any measurements from their urine samples.

Post-testing will be the same as pre-testing and will commence after the 10- or 12-weeks (pending soccer season length). All measures described above in Pre-Intervention testing will take place again, with the exception of a week of Fitbit® monitoring following completion of the 10- or 12-week (pending soccer season length) intervention.

Debrief: Following completion of post-intervention testing, participants will be debriefed (see Debrief Document in Other Documents) regarding the sham urine collections which were used to increase adherence.

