### **Procedures:**

**Informed Consent, Parental Permission and Assent:** These will be obtained over Zoom, prior to participation in any study procedures.

**Randomization:** Randomization will occur following pre-intervention testing. Participants will be randomized via random number generator stratified by sex, and blinded into either whey protein supplement group or placebo (isocaloric) control group.

**Pre- and Post-Intervention Testing Background:** Pre- and post-intervention testing will occur over a single day for each participant at the University of Utah campus. There will be three (3) separate days of pre-intervention and post-intervention testing. One day will be for members of the “Girls’ Soccer Team”. One day for members of the “Boys Soccer Team”. The final day will be a make-up day for participants who were unable to attend with their team, but wish to participate. According to the coaches, no student-athletes openly identify as non-binary nor transgender. However, in March of 2020 Idaho’s “Fairness in Women’s Sports Act” was signed in to law. While it has yet to go in to effect, if taken up, it will prohibit transgender women and girls from competing on teams that align with their gender identity in Idaho. Thus, it is possible that individuals may not be open about this. To address concerns re: outing anyone, participants will complete the testing day on their team’s assigned day, as mentioned above, or on the make-up day if they are not available on the main testing day. Furthermore, our strategy of having make-up testing options for both pre- and post-intervention means that not all members of each team will be tested on the same day. Thus, this mitigates potential risk of coercion as teammates will not know for sure who elected to participate or not in the trial.

**Selection of School:** Marsh Valley High School in Marsh Valley, ID was selected as the test site for this study due to the following connection:

The Track and Field coach at this school comes from a family of Dairy farmers and is also a Paralympic athlete who has had a relationship with the Western Dairy Center (study sponsor) for a number of years. He inquired with WDC about doing a trial on his student-athletes, so the WDC connected the PI ([name]) with this school for the trial. Due to large differences in athlete type and training load in track and field (sprinters, distance, jumpers, throwers),

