utilizing the track and field team was not a good scientific decision. Thus, we elected to conduct this study on adolescent soccer players.

**Travel to the University of Utah:** Travel via charter buses from Marsh Valley High School in Marsh Valley, ID to the University of Utah, and back to Marsh Valley will be provided free of charge to participants. We will utilize Salt Lake Express bus charter, which is the transportation provider for Marsh Valley High School athletics. The University of Utah's Risk Management Department does not have concerns with this transportation modality (see emails in Other Documents). The charter bus will be paid for utilizing grant funding awarded to the PI ([name]) from the study sponsor (Western Dairy Center).

**Pre-Intervention Procedures:** Before both testing days (pre- and post-intervention) we will ask that all participants record their diet and exercise for 2 days leading up to each of these visits. We will ask that they perform the same diet and activity behaviors that they report before the baseline intervention testing day for the post-intervention testing day. The morning of testing days, before departure from Marsh Valley High School, we will have them consume a study provided granola bar. The granola bar is a Chocolate Chip CLIF BAR® containing 250 calories. Allergens include soy, and may contain peanuts, tree nuts, milk, sesame, and wheat. Student-athletes will report to the Skeletal Muscle Exercise Research Facility in the morning, where they will undergo the following measures:

**Questionnaires:** Athletes will fill out gastrointestinal (GI) and sleep questionnaires. Specifically, the Munich Chronotype Questionnaire (MCTQ) (Shahid, Wilkinson, Marcu, & Shapiro, 2011), Pittsburg Sleep Quality Index (PSQI) (Smyth, 1999), a GI symptom questionnaire (Pereira, Dora IACouto Irving, Susana SLOmer, Miranda CE Powell, Jonathan J. 2014). Participants will fill out a 3-day, 24-hour ASA diet recall at baseline. This data will be uploaded to REDcap.

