### **Procedures performed for research purposes only:**

## **Statistical Methods, Data Analysis and Interpretation**

---

A two-way (group x time) repeated measures analysis of variance (ANOVA) will be used to compare change between groups in body composition, performance, and recovery. If a significance in group x time interactions occur, an independent t-test will be performed for each dependent variable between groups. An alpha level will be set at  $p < 0.05$ .

Sample size and power analysis: For a total of 60 participants, we anticipate a 30% attrition, leaving us with  $n=40$  ( $n=20$  per group). This provides  $>90\%$  power for detecting differences in our main outcome variables. Based on preliminary data, a similar study used  $n=18$  for their sample sizes. This sample size will be used for sample size calculations for a future well-

powered trial. Estimates for effect sizes will be implemented due to the limited sample size. Effect sizes ( $n^2$ ) will be defined as small (0.20), medium (0.50), and large (0.80).

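### DOMS has no baseline but is tested only through a group x time interaction, so a soreness difference complete by week 2 and then constant would pass the gate in only about 5% of trials

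*Combined protocol and SAP*

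**What the plan says.** All references are to the combined protocol and SAP.

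- **Baseline.** Under Procedures (Questionnaires), "Athletes will fill out gastrointestinal (GI) and sleep questionnaires". The forms then named are the MCTQ, the PSQI and a GI symptom questionnaire, with a diet recall. DOMS is not named.
- **Randomization.** Also under Procedures: "Randomization will occur following pre-intervention testing", stratified by sex.
- **In season.** Under INTERVENTION (Questionnaires), the "Pittsburgh Sleep Quality Index (PSQI), DOMS questionnaire" and the GI form "will be completed at 2-, 4-, 6-, 8-, 10-, and potentially 12-weeks (pending soccer season length"). This is the only place where DOMS appears.
- **Post-testing.** Under INTERVENTION: "Post-testing will be the same as pre-testing and will commence after the 10- or 12-weeks". It repeats a battery without DOMS.
- **Analysis.** Under Statistical Methods, Data Analysis and Interpretation, the model has two factors, group and time, and is described in these words: "repeated measures analysis of variance (ANOVA) will be used to compare change between groups in body composition, performance, and recovery". The independent t-test between groups follows "If a significance in group x time interactions occur". No group main effect, average over visits or separate DOMS model is given a role.

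**The concern.** When the first time point precedes treatment, a group x time interaction picks up a treatment effect, because the arms start level and then separate. When every time point is on treatment, the same term measures only whether the gap between arms changes from one visit to another. A gap that is in place at the first visit and stays put is invisible to it.

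DOMS is in that second position. It is the only soreness measure in the trial, and Background and Introduction cites reduced soreness after exercise as part of the rationale for protein. Recovery is in the overall aim and main hypothesis under Purpose and Objectives. The documents do not define recovery or assign DOMS to it, but the inference is reasonable. At stake is whether the stated rule can recognise a real soreness difference in data that would otherwise be adequate to show a large one.

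**Working it through.** **Inputs from the plan.** 60 enrolled and 40 analysed, 20 per group; alpha 0.05 (Statistical Methods). DOMS at weeks 2, 4, 6, 8 and 10, so k = 5 visits, or 6 if week 12 is used (INTERVENTION).

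**Assumptions (not in the plan).** Equal variance at each visit, set to 1; within-person correlation rho of 0.3 to 0.7; compound symmetry, with AR(1) as a check; two-sided testing; complete data. Differences of 0.5 and 0.8 SD are illustrative.

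**The plan's own figure.** It states more than 90% power but gives no effect size, SD or named outcome, so the figure cannot be reproduced. For scale, a single-time comparison of 20 per arm reaches 90% power at d = (1.960 + 1.282) x sqrt(2/20) = 1.03. At d = 0.8 it has 72% power, and at d = 0.5 it has 35% (normal approximation).

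**Step 1: the planned interaction test.** Let delta_t be the arm difference at visit t. Under compound symmetry the interaction F test has k-1 = 4 and 38 x 4 = 152 degrees of freedom, and noncentrality

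lambda = (n/2) x sum of (delta_t - mean delta)^2 / (1 - rho).

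If delta_t is the same at all visits, each bracket is zero and lambda = 0, for any rho and any size of difference. The test then rejects at its type I error rate.

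Simulation (10,000 trials per scenario, 5 or 6 visits, constant 0.5 or 0.8 SD):

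| Structure | Interaction significant |
|---|---|
| Compound symmetry, uncorrected | 4.5-5.3% |
| Compound symmetry, Greenhouse-Geisser | 4.0-4.6% |
| AR(1), uncorrected | 5.3-7.6% |
| AR(1), Greenhouse-Geisser | 4.3-4.8% |

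The miss rate is therefore about 92-96%.

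**Step 2: the group contrast averaged over visits.** The variance of a person's mean score is (1 + (k-1) rho)/k, and the noncentrality is d / sqrt(variance x 2/20). For k = 5:

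| rho | Variance of mean | Noncentrality, d = 0.8 | Simulated power, d = 0.8 | Simulated power, d = 0.5 |
|---|---|---|---|---|
| 0.3 | 2.2/5 = 0.44 | 3.81 | 96% | 64% |
| 0.5 | 3.0/5 = 0.60 | 3.27 | 89% | 51% |
| 0.7 | 3.8/5 = 0.76 | 2.90 | 81% | 42% |

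The noncentral t distribution on 38 degrees of freedom gives 96%, 89% and 81% at 0.8 SD, and 64%, 51% and 42% at 0.5 SD. Under AR(1), with 5 or 6 visits, the simulated ranges are 88-99% or more at 0.8 SD and 50-84% at 0.5 SD.

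**Step 3: differences that change over time.** Five visits, compound symmetry, interaction test uncorrected.

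- Linear growth to 0.8 SD at week 10 (0.16, 0.32, 0.48, 0.64, 0.80): the squared deviations sum to 0.256, so lambda = 10 x 0.256/(1 - rho) = 3.66, 5.12 and 8.53 for rho 0.3, 0.5 and 0.7. Simulated power is 28%, 39% and 62%.
- No difference at week 2, then 0.8 SD from week 4: the sum is 0.512, so lambda = 7.31, 10.24 and 17.07. Simulated power is 56%, 71% and 93%.

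So the near-total loss in Step 1 belongs to one pattern: complete by week 2, then flat.

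**Step 4: would a baseline alone cure it?** With a baseline visit added, a constant 0.8 SD difference thereafter and the interaction gate kept, simulated power is 52%, 69% and 92% for rho 0.3, 0.5 and 0.7. At 0.5 SD it is 21%, 29% and 49%. This helps, but depends heavily on rho.

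**The case against.** Several points on the other side are fair.

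- **A reader might infer that any steady improvement in soreness would be missed.** It would not. A benefit that builds up during the season is partly visible to the interaction (Step 3).
- **A reader might take the flat pattern to be the most plausible one.** The documents give no time course for soreness. The rationale cites an effect of protein after an exercise session, which fits early onset. The hypothesis speaks of changes following the 10-week period, which fits a gradual build-up equally well.
- **A reader might conclude that the trial would report no effect on recovery.** That goes beyond the text. A two-way ANOVA produces a group term as standard output, the plan does not forbid reporting it, and effect-size estimates are promised. A constant difference could surface that way. What remains is that the group term has no prespecified inferential role, so turning to it after a null interaction would be post hoc.
- **Recovery is not untestable as a whole.** The blood markers of inflammation and muscle growth have pre and post values, for which the interaction works as intended.
- **PSQI, Fitbit sleep and GI scores are also repeated in season.** They have baselines, so this defect does not apply to them.
- **The 5% is alpha by construction, not an empirical finding.** This is correct, and it is why the result does not depend on effect size. The power of the alternative contrast does rest on assumed correlations.

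None of this removes the core problem for DOMS.

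**Conclusion.** The concern holds for DOMS and for one pattern of benefit. Because every DOMS score is on treatment, the stated gate tests change in the arm difference after week 2. A difference complete by week 2 and constant thereafter would pass it at about the alpha rate: about 5%, or up to about 8% uncorrected under AR(1). That conclusion follows from the form of the test and does not depend on the size of the benefit. The comparison with an averaged contrast (81-96% power at 0.8 SD, 42-64% at 0.5 SD) assumes 20 per arm, five visits, compound symmetry and a correlation of 0.7 to 0.3. Treating DOMS as a recovery outcome is an inference. The documents do not support extending the finding to gradual benefits, to recovery as a whole, or to the sleep and GI measures.

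**What to change.** In Statistical Methods, Data Analysis and Interpretation, state that DOMS will be analysed as the between-group difference in mean score over the on-treatment visits. This is a 1-df contrast, for example from a mixed model with visit, group and sex (the stratification factor), tested at 0.05 and reported with a confidence interval whatever the interaction shows. State whether week 12 enters the average if the season runs that long. The group x time term can be kept as a secondary description of time course.

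The comparison is valid under randomization without a baseline. Adding the DOMS form to the baseline questionnaires and using it as a covariate is optional. Its value is uncertain, because the consent-process section places baseline testing outside the soccer season and soreness then may predict in-season soreness poorly. Adding a baseline while keeping the interaction gate is not a substitute (Step 4).

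The cost is a sentence or two of SAP text, written before unblinding, with no new data collection. The optional baseline form would add slight participant time to an existing session.

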
## Purpose and Objectives

---

The overall aim of the proposed project is to compare protein supplementation on performance, recovery, and body composition changes in adolescent soccer players between the whey protein and the control group in response to the 10-week intervention. Hypothesis: We hypothesize that the whey protein group will demonstrate more favorable changes in

performance, recovery, and body composition outcomes than the control group following the 10-week supplementation period.

Secondary outcomes will include investigating interactions between sleep physiology and dietary protein on muscle recovery and performance following the 10-week intervention.

*Hypothesis:* Sleep efficiency will be higher in the whey protein supplementation group versus the placebo control. *Exploratory* analyses will examine the impact of whey protein supplementation on dimensions of sleep including duration, regularity, satisfaction, alertness, timing, and sleep staging (e.g., stage N1, N2, SWS, rapid eye movement (REM))

The **expected outcomes** will provide support for whey protein supplementation to enhance exercise performance, recovery, and body composition in adolescent, team-sport athletes. Completion of the proposed objectives (see below) will add to the sparse evidence base on protein supplementation in this unique, athletic population, and provide preliminary data for future investigations in this area. Specifically, future work could address both mechanistic questions as well as evaluation of other protein options, such as milk consumption, which could be a more cost-effective and acceptable option for youth athletes.

Objective 1: Compare the impact of 10-weeks of whey protein vs. isocaloric control on performance in high school soccer players.

Objective 2: Compare the impact of 10-weeks of whey protein vs. isocaloric control on body composition in high school soccer players.

Objective 3: Compare the impact of 10-weeks of whey protein vs isocaloric control on hunger and satiety in high school soccer players

Objective 4: Compare the impact of 10-weeks of whey protein vs. isocaloric control on sleep duration and quality in high school soccer players.

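### GI symptoms are collected throughout but sit in no objective or stated analysis, and reasons for stopping product are not recorded, so no between-arm tolerability result is planned

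*Combined protocol and SAP*

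**What the plan says.** **Collection.** At pre-intervention testing, "Athletes will fill out gastrointestinal (GI) and sleep questionnaires". On product, the Questionnaires paragraph of the INTERVENTION section says "the GI symptom questionnaire will be completed at 2-, 4-, 6-, 8-, 10-, and potentially 12-weeks". At the end, "Post-testing will be the same as pre-testing", so the form is given again. On handling, the same section says "Study personnel will send questionnaires to participants and will use REDCap to complete the questionnaires".

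**Use.** Purpose and Objectives gives an overall aim, hypotheses, secondary and exploratory sleep questions, and four objectives: performance, body composition, hunger and satiety, and sleep. GI symptoms and tolerability are not among them. In Statistical Methods, Data Analysis and Interpretation, a group-by-time repeated measures ANOVA is planned to "compare change between groups in body composition, performance, and recovery". No GI score, summary or arm comparison is defined.

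**Stopping and loss.** The INTERVENTION section provides surplus packets, an intake checklist that also records lost packets, and monthly collection of empty containers, all to measure compliance. No item asks why product was stopped, and no adverse-event question appears. The statistical section expects 30% attrition. The first Inclusion Criteria paragraph ties the primary-outcome analyses to 40 participants who complete the whole protocol.

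**Intended conclusion.** The expected outcomes "will provide support for whey protein supplementation to enhance exercise performance, recovery, and body composition in adolescent, team-sport athletes".

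**The concern.** The Background says the effect of this strategy in teenage athletes is unknown, and participants take product twice a day for 10 or 12 weeks. The plan specifies how benefit will be compared between arms but not how tolerability will be. A favourable report could then carry no tolerability result, or one whose score, time points and population were chosen after the data were seen.

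Missing reasons for stopping are the more serious gap. A GI comparison could be built later from the stored forms. The reason a participant gave up the product cannot be recovered once it has gone unasked. If whey, or the control, is poorly tolerated, the participants affected are among those most likely to leave, and they would be counted with everyone else who leaves.

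**Working it through.** **1. Where each item is collected and where it is used**

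- GI symptoms: collected at baseline, weeks 2, 4, 6, 8, 10 and possibly 12, and post-test. Used in no objective and not in the stated analysis.
- Adverse events: no item in the supplied text.
- Reason for stopping product: no item. Packet counts and the checklist can show that intake stopped, but not why.
- The delayed-onset soreness form, the sleep index and the blood markers serve recovery, sleep and mechanism. The GI form is thus the only instrument that reads as a tolerability measure.

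**2. Expected loss**

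- The plan's figure: 60 × (1 − 0.30) = 42, against the stated 40. This agrees within rounding; 40 of 60 implies 20/60 = 33% loss.
- Participants leaving with no recorded reason: 60 × 0.30 = 18, or 60 − 40 = 20. With equal allocation (assumed), that is 9 to 10 per arm.

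**3. Exposure before the forms**

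- Two doses a day: 2 × 14 = 28 doses before the week-2 form. The total is 2 × 70 = 140 over 10 weeks or 2 × 84 = 168 over 12.

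**4. What a GI comparison could show**

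The documents give no symptom rates. The rates of 10% and 30% below are assumptions for illustration.

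- 95% half-width at 20 per arm: 1.96 × √[(0.10 × 0.90 + 0.30 × 0.70)/20] = 1.96 × √0.015 = 0.240, or 24 points.
- At 30 per arm: 1.96 × √(0.30/30) = 0.196, or about 20 points.
- Power at two-sided 0.05 with 20 per arm: about 35% by normal approximation, 24% by Fisher's exact test. Reaching 80% needs 62 per arm by normal approximation.
- For assumed rates of 10% and 50% at 20 per arm: about 81% (Fisher 74%).
- Zero events of some kind in one arm: the one-sided 95% upper bound is 1 − 0.05^(1/n), which is 13.9% for n = 20 and 9.5% for n = 30.

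The comparison is therefore an estimate with an interval. It cannot show absence of harm. Using everyone dosed instead of completers narrows it somewhat and, more importantly, keeps in those who left.

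**5. The ±1 week allowance**

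The INTERVENTION section lets time points vary by ±1 "week to allow for scheduling flexibility". If this covers the two-weekly forms:

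- smallest gap between the week-2 and week-4 forms: (4 − 1) − (2 + 1) = 0 weeks;
- largest gap: (4 + 1) − (2 − 1) = 4 weeks;
- a week-10 form could fall at week 11, after product ends in a 10-week season.

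The sentence closes the paragraph on packet collection and precedes the Questionnaires paragraph, so its scope is uncertain.

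**The case against.** Four points have force.

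- **The document is incomplete.** Some pages were removed before review, and the protocol refers to other study documents that were not supplied. A reader might infer that nobody acts on the GI answers. The text does not say so. It only names no one who reviews them, and a procedure may exist elsewhere.
- **There are other contacts.** Study personnel meet participants at monthly distribution and collection, some give urine at weeks 4 and 8, and families are told they may withdraw at any time. A reader might infer that the GI form is the only route by which a problem could surface, or that a symptomatic player would carry on unnoticed. These contacts, with the packet counts and checklist, contradict that. None of them, however, is described as recording a symptom or a reason for stopping.
- **The analysis list is not exhaustive.** It does not name sleep or hunger and satiety either, although both are stated objectives. Omission from it does not prove that GI data will go unanalysed. But sleep and hunger are at least objectives, and GI symptoms are neither an objective nor listed. The GI form might be meant for the hunger and satiety objective, for which no other instrument is evident, but nothing says so.
- **The trial is preliminary.** The plan says it will inform a future well-powered trial, and dairy allergy is already an exclusion. This argues for a modest descriptive analysis, but it does not remove the need to record why people stop.

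**Conclusion.** The concern holds in a limited form. In the supplied text, GI symptoms are measured repeatedly in both arms without a planned use, and neither adverse events nor reasons for stopping product are asked about. Some 18 to 20 of 60 participants are expected to leave, and any share due to intolerance could not be identified.

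The documents do not support the stronger reading that harm would go unseen or that reporting it is ruled out; a post hoc GI comparison would remain possible. What is missing is a pre-specified comparison, and information that cannot be collected afterwards.

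The finding does not depend on the illustrative figures. Those rest on equal allocation, all 60 being randomised, and assumed symptom rates. They show only that the tolerability result should be descriptive. The effect of the ±1 week allowance is conditional on its applying to the forms. This is an inexpensive improvement that should be made, and it does not invalidate the design.

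**What to change.** 1. Name the GI symptom score as a tolerability outcome and define how it is scored. Report it by arm over the on-product forms, adjusted for baseline, as a difference with a confidence interval, in every randomised participant who took at least one dose. State that it is descriptive and not a test of no harm.
2. Add two items to the existing two-weekly REDCap form: one on adverse events, and one asking whether product was stopped and why. Tabulate both by arm.
3. State which study role reviews the answers while participants are still on product. Any symptom threshold or resulting action is for the investigators to set.
4. State whether the ±1 week allowance applies to the REDCap forms.

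The cost is protocol wording, two form items, one extra table and a little staff time for review. Sample size, visits and existing instruments are unchanged.
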